Patients will be offer the opportunity to consent in their pre-surgical appointments. They may also consent on the day of surgery or any day up until that day by contacting the clinical coordinator.

What steps will be taken in that location to protect the privacy of the prospective participant?

Consent will be given in clinical care areas of Duke (i.e. in exam rooms) and so privacy should be protected along with and at the same level as all other clinical care.

How much time will be allocated for conducting the initial consent discussion, including presenting the information in the consent document and answering questions, with each prospective participant?

Patients will have as long as they desire to discuss their participation and will then be able to follow up in writing or by phone with the clinical coordinator. Approximately 20-30 minutes will be allocated in addition to their regular appointments. The clinical coordinator will be available for follow up by phone or email.

What arrangements will be in place for answering participant questions before and after the consent is signed?

The attending surgeon and clinical coordinator will be available during the initial approach of the subjects for consent. The clinical coordinator will be available by phone or email to follow up with patients to answer questions. The Duke Center for Hyperbaric Medicine and Environmental Physiology is accessable to patients by appointment and patients may choose to visit the facility prior to their surgery to see the chambers and meet chamber staff.

Describe the steps taken to minimize the possibility of coercion or undue influence.

No compensation will be given to patients for this study. There is no incentive for patients to enter into the study beyond the possibility that they may receive and benefit from HBO₂.

As much as possible all care is standardized from one patient to the next such that the only difference in care received by patients is that which is medically necessary for individual conditions. Hence, there is no benefit or loss for patients whether they are in the study or not.

Patients will be consented as early as possible so that patients have the longest time between entering into the study and the beginning of treatment to consider their involvement. Since patients may withdraw from the study at any time, this should limit any time pressure or other situational influence that may arise during the initial consent process.

What provisions will be in place to obtain consent from participants who do not read, are blind or who do not read/understand English?

Patients who are not able to read the consent form themselves will be offered translation services, sign interpretation, or other helpful adaptive services to facilitate communication of information about the study and the consent process to them. Blind or non-reading patients may choose to have the consent read aloud. In no case will study subjects be allowed to have consent given for them. Each participant must be able to consent for themselves so every effort will be made to provide all information needed for consent to patients directly.

Do you plan to obtain written consent for the conduct of research?

● Yes O No	
Protected Health Information (PHI)	
Indicate how you intend to use potential subjects' Protected Health Information (PHI):	
 I will review, but not record, PHI prior to consent. I will record PHI prior to consent. I do not intend to use PHI prior to consent. I will record PHI without consent. (decedent research, database repository, chart review) 	
Review Preparatory to Research (RPR)	
Describe the specific PHI that will be reviewed to prepare a research protocol and/or to ascertain and recruit subjects:	/or
Patient PHI may be reviewed to determine eligibility prior to their consent for the study. This will occur in conjunction with their normal preoperative care.	
Principal Investigator's Affirmation:	
The PHI is necessary for the purposes of this activity.	
Drugs, Biologics, and Other Substances	
Select Protocol Phase (for studies with FDA regulated drugs or biologics only). Choose only one:	
 ○ Phase 0 ○ Phase I ○ Phase I/II ○ Phase II / III ○ Phase III / III ○ Phase IV ○ N/A ○ Pilot 	

Drugs, biologics, or other substances being evaluated as a part of this research study:

Add all drugs, biologics, or other substances being evaluated as a part of this research study for which an IND is provided for the indication used in this study.

Also add any other drugs, biologics or other substances here that are being used as a part of this research study, for which an IND is not provided.

List every other drug, biologic or other substance for which side effects are described in the consent form.

View Details	Drug Name		FDA Approved	A new drug or a new use of approved drug:	IND Number	
	Drug/Biologic /Substance Generic Name: Generic Drug Name: Investigational Drug Name:		Yes	No		
Drug/Biologic/Substance Generic Name:		Hyperbaric oxygen				
Generic Drug Name:						
Investigational Drug Name:						
Drug/Biologic/Substance Source:						
Is the drug/substance being provided to the subject free-of-charge?		Yes				
Is the Drug FDA Approved?:		Yes				
Is this drug/biologic or other chemical, metabolite, nutritional substance or other substance to be used in this research subject to the provisions of the Controlled Substances Act?		No				
Does this Drug have an IND Number?		No				
IND Number						
IND Holder:		N/A				
IND details:						
If FDA Approved and an IND is not required, Please provide a rationale for exemption:		Medical grade oxygen is used for this study.				
Will drug/substance be shipped from Duke to external locations		No				
Dose Range:		2 ATA/2 hours				
Frequency:		2x daily				
Will this drug, biologic, chemical, metabolite, nutritional substance or other substance be manufactured or compounded at Duke?		No				
Drug Storage Restrictions (including temperature, etc.):		N/A	N/A			
As indicated in the Investigator's Brochure or other available						

highest FDA Use-in-Pregnancy Rating for drug used for research purposes in this study?:							
Are you using an investigational pharmacy at Duke?							
Please be aware that inpatient administration of an investigational drug requires the use of the Duke IDS or Oncology ICS, as per Department of Pharmacy policy. O Yes No							
Who will be responsible for the storage, inventory and control of the drug/biologic or other chemical, metabolite, nutritional substance or other substance to be evaluated in this research?							
The IDS is available to assist any investigator (upon request) with storage and control of investigational drugs in the outpatient setting							
The oxygen to be used in this study is standard medical grade oxygen, from the same source as all Duke patients receive (see uploaded document).							
Where will the drug/biologic or other chemical, metabolite, nutritional substance, or other substance to be evaluated in this research be stored?							
N/A							
From where will the drug/biologic or other chemical, metabolite, nutritional substance or other substance to be evaluated in this research be dispensed?							
Duke Center for Hyperbaric Medicine & Environmental Physiology							
At the completion of this research study, what will be done with the unused or returned investigational drug /biologic or other chemical, metabolite, nutritional substance or other substance?							
N/A							
Privacy and Confidentiality							
Explain how you will ensure that the subject's privacy will be protected:							
Consider privacy interests regarding time and place where subjects provide information, the nature of the information they provide, and the type of experience they will be asked to participate in during the research.							
All information will be protected and PHI will be handled in accordance with all DUke policies and procedures. Redcap will be used for data collection and storage and primary documents will be stored in the study binder kept in a locked cabinet in the Duke Hyperbaric lab. Patients will be consented and have the ability to ask questions in patient care areas where curtains, exam rooms, and other strategieis for protecting patient confidentiality will be used to protect patient privacy.							
Describe how research data will be stored and secured to ensure confidentiality:							
How will the research records and data be protected against inappropriate use or disclosure, or malicious or accidental loss or destruction? Records and data include, for example, informed consent documents, case report forms or study flow sheets, survey instruments, database or spreadsheets, screening logs or telephone eligibility sheets, web based information gathering tools, audio/video/photo recordings of subjects, labeled specimens, data about subjects, and subject identifiers such as social security number.							

Data will be stored using the Duke redcap system. Primary data that is in paper form will be stored in the study binder kept in a locked cabinet. All correspondence regarding the program will occur through the Duke email system.

Application Questions Complete

Please click Save & Continue to proceed to the Initial Submission Packet.

The Initial Submission Packet is a short form filled out after the protocol application has been completed. This is an area to attach protocol-related documents, consent forms, and review the application.

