After informed consent is obtained, patients will be assigned to either a treatment group or a standard care group. Because of the nature of the treatment blinding is not possible. Patients will be informed of their group assignement when they arrive on the floor after surgery. Each patient in the treatment group will receive ${\rm HBO}_2$ treatments in the Duke Center for Hyperbaric Medicine and Environmental Physiology using normal treatment protocols already established and approved by DUHS for the administration of HBO $_2$. Treatments will be given twice per day until the patient is discharged or 10 treatments are given.

Treatments will consist of breathing 100% O $_2$ through a head tent while inside a hyperbaric chamber at 2 ATA for 2 hours. Hyperbaric chambers at Duke allow for the presence of nursing staff and emergency access into the chamber while treatment is ongoing. Patients will experience a 15 minute compression and 5 minute decompression phase.

The Vascular Quality Initiative (VQI) is a multicenter voluntary reporting system for outcomes related to vascular surgery. The primary outcome of this study, postoperative complications, will be those outcomes meeting the definition set out in the VQI data dictionary, the set of definitions for inclusion in the VQI databse. This allows for a standard definition of complications recognized by a majority of academic medical centers across the country.

Secondary outcomes will include: Hospital length of stay, 90-day mortality, failure to heal at 4 and 8 week follow-up visits and ability to ambulate with a prosthesis at 6 months post amputation. Patients will be examined daily during their inpatient stay and then at 4 and 8 week follow-up visits once discharged from the hospital. Periwound transcutaneous oxygen presures will be taken prior to administration of HBO₂ and at the completion of 10 treamtents.

The statistical plan for this study will test non-directional hypotheses (two-sided tests). Bonferroni correction will be used to adjust for multiple tests. SAS 9.4 (SAS Institute, Inc.) will be used to analyze the data. The main analysis of the primary efficacy hypotheses will include data from all randomized patients in the group to which random assignment is made. Hence, the analysis will be intention to treat, and regardless of subsequent events and every effort will be made to continue to follow all patients that begin the study.

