Proportions and differences in proportions in the difference complication rate requiring reoperation in 30 days will be estimated along with 95% confidence interval. The difference in reoperation rates will be examined using Z-test. The analysis is similar for secondary outcomes. Exploratory outcome of 90-day mortality in the two treatment groups will be determined using Kaplan-Meier techniques with log-rank test. The Cox proportional hazards model will be used to determine the predictors of survival. Model assumptions will be examined and goodness of fit of these models will be assessed.

Because studies of this type have not been conducted before an effect size is difficult to estimate. However, based treatment of diabetic foot ulcers with HBO2¹ it is hoped that an effect size of 0.62, or reduction of complications by 60% can be seen. 80% power will be acheived by randomizing 40 subjects into each of the treatment and standard care groups. Hence, 80 subjects will be needed for this study. Given the high volume of operations conducted at Duke this should be achievable in less than 3 years. Midpoint analysis may produce results even sooner than that.

Selection of Subjects

• List inclusion/exclusion criteria and how subjects will be identified.

The subject selection will be equitable and all relevant demographic groups will have access to study participation (per 45CFR46.111(a)(3), 21CFR56.111(a)(3)).

Inclusion Criteria

- 1. Patients over the age of 18
- 2. Able to Consent
- 3. Have been identified as having a non-traumatic indication for amputation surgery of lower limb
- 4. Be cleared and scheduled for surgery for below-knee amputation of lower limb at Duke University Hospital
- 5. Be able to receive HBO₂ therapy.

Exclusion Criteria

- 1. Unable to consent
- 2. Unable to receive hyperbaric oxygen
- 3. No longer need to receive surgery for amputation of lower limb
- 4. Patients with End Stage Renal Disease on dialysis
- 5. Patients with current renal failure as measured by creatinine levels vs baseline change of more than 1 mg/dL and for whom dialysis is expected to be required within the next month
- 6. Patients with Calciphylaxis
- 7. Patients with traumatic injuries that are the cause of the amputation

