- 8. Patients with cancer being treated by chemotherapy, scheduled to be treated, or being treated or scheduled to be treated by radiation.
- 9. Patients with limb amputation secondary to ischemic complications from other operations.
- 10. Patients undergoing a revision or reoperation on prior below-knee amputation
- 11. Patients undergoing above-knee amputation after prior below-knee amputation

Subject Recruitment and Compensation

Describe recruitment procedures, including who will introduce the study to potential subjects. Describe
how you will ensure that subject selection is equitable and all relevant demographic groups have access

to study participation (per 45 CFR 46.111(a) (3)). Include information about approximately how many DUHS subjects will be recruited. If subjects are to be compensated, provide specific prorated amounts to be provided for expenses such as travel and/or lost wages, and/or for inducement to participate.

Subjects will be recruited at DUH. Surgeons will identify subjects and refer them to the study coordinator for enrollment. All subjects will receive their surgery at Duke University Hospital. Any patient meeting the criteria will be accepted for the study. All relevant demographic groups have access to study participation (per 45CFR46. 111(a)(3), 21CFR56.111(a)(3)).

Until this point the number of patients coming through the outpatient clinic for primary amputation is very limited. Rather, the majority of patients requiring below-knee amputation have been going directly to the ED and being admitted. In mid-November one of the KPs will be transitioning to a new position with the inpatient vascular team, which is expected to greatly increase the opportunity to find eligible patients and discuss the study with them. She plans to develop a system to have the Vascular Surgery census reviewed twice per week to identify patients who may be eligible for the study.

Consent Process

• Complete the consent section in the iRIS Submission Form.

Subject's Capacity to Give Legally Effective Consent

• If subjects who do not have the capacity to give legally effective consent are included, describe how diminished capacity will be assessed. Will a periodic reassessment occur? If so, when? Will the subject be consented if the decisional capacity improves?

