The statistical plan for this study will test non-directional hypotheses (two-sided tests). Bonferroni correction will be used to adjust for multiple tests. SAS 9.4 (SAS Institute, Inc.) will be used to analyze the data. The main analysis of the primary efficacy hypotheses will include data from all randomized patients in the group to which random assignment is made. Hence, the analysis will be intention to treat, and regardless of subsequent events and every effort will be made to continue to follow all patients that begin the study.

Proportions and differences in proportions in the difference complication rate requiring reoperation in 30 days will be estimated along with 95% confidence interval. The difference in reoperation rates will be examined using Z-test. The analysis is similar for secondary outcomes. Exploratory outcome of 90-day mortality in the two treatment groups will be determined using Kaplan-Meier techniques with log-rank test. The Cox proportional hazards model will be used to determine the predictors of survival. Model assumptions will be examined and goodness of fit of these models will be assessed.

Based on randomized control trials of ${\rm HBO}_2$ effects on healing diabetic foot ulcers this study is proposed to achieve 80% power to detect an effect size of 0.62, or reduction of complications by 60% by randomizing 40 subjects into each of the treatment and placebo groups. Hence, 80 subjects will be needed for this study. Given the high volume of operations conducted at Duke this should be achievable in less than 3 years.	
Data & Safety Monitoring	
 Summarize safety concerns, and describe the methods to monitor research subjects and their data to ensure their safety, including who will monitor the data, and the frequency of such monitoring. If a data monitoring committee will be used, describe its operation, including stopping rules and frequency of review, and if it is independent of the sponsor (per 45 CFR 46.111(a) (6)). Clinical and demographic data will be collected electronically and stored using Duke University's Redcap system. Information pertaining to blinding, patient treatment, or any other study information that may arise incidentally will be stored in the Duke hyperbaric treatment facility in a locked cabinet in the nurse manager's office. 	
Privacy, Data Storage & Confidentiality	
Complete the Privacy and Confidentiality section of the iRIS submission form.	
Study Scope	

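### Six-month prosthetic ambulation is compared without using pre-amputation walking status; recording it and stratifying on it would be a cheap gain in power for this secondary outcome

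*Combined protocol and SAP*

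**What the plan says.** The secondary objectives and Design & Procedures list "ability to ambulate with a prosthesis at 6 months post amputation" as a secondary outcome. No definition of ambulation, scoring rule or denominator is given for it.

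Under Selection of Subjects, the surgical criterion is "Be cleared and scheduled for surgery for below-knee amputation of lower limb at Duke University Hospital". None of the five inclusion or eleven exclusion criteria concerns walking, prosthesis candidacy or the other leg. The two that mention an earlier amputation exclude only revision or reoperation of a below-knee amputation and above-knee amputation after one. Subject Recruitment adds: "Any patient meeting the criteria will be accepted for the study".

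For the primary comparison, Design & Procedures and Data Analysis & Statistical Considerations give proportions, their difference and a 95% confidence interval, and then "The difference in reoperation rates will be examined using Z-test". The next sentence is "The analysis is similar for secondary outcomes". The main analysis of the primary hypotheses "will include data from all randomized patients in the group to which random assignment is made". The plan also says "Bonferroni correction will be used to adjust for multiple tests", without the number of tests. Baseline walking status is not collected, stratified on or adjusted for anywhere.

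**The concern.** Whether a patient walked before amputation is likely to be a strong determinant of whether that patient walks on a prosthesis six months later. The criteria admit patients who did not walk, and the planned comparison ignores the distinction.

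If a share of each arm has little prospect of success whatever the wound does, both proportions fall and so does the absolute difference that the plan estimates. With 80 patients there is little power to spare. A null ambulation result would also be hard to read, because nobody could tell how many patients had a realistic chance of responding. The status has to be collected prospectively: the trial is unblinded, so a status abstracted later would be open to influence from knowledge of the arm.

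**Working it through.** **The plan's own figure.** No power is stated for ambulation. The 40 per arm is for the primary outcome and reproduces from a standardized effect of 0.62: n = 2(1.96 + 0.842)²/0.62² = 2 × 7.85/0.3844 = 40.8, so 41 per arm; power at 40 is 79.2%.

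**Inputs.** From the documents: 40 per arm, two-sided testing, difference in proportions with a Z-test. Assumed: alpha 0.05 (from the 95% interval), a share f = 10-40% of prior non-walkers, and the walking rates. Two effects among prior walkers are used:
- 50% versus 80%, a large effect.
- 50% versus 66.6%, tied to the plan. The local complication rate is 27/98 = 27.6% (for all lower limb amputations) and the hoped-for reduction is 60%, so 0.60 × 27.6 = 16.6 points. If HBO₂ helps walking only by preventing complications, and every complication prevented yields a walker, the gain is at most about 16.6 points.

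**Dilution.** If all prior non-walkers fail, a rate p becomes p(1 − f) in each arm and the difference shrinks by the factor (1 − f). The risk ratio is unchanged in expectation.

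**Power.** Unadjusted: exact enumeration of the pooled Z-test at p(1 − f), 40 per arm. Stratified: Cochran-Mantel-Haenszel test (N − 1 variance, no continuity correction), exact enumeration averaged over binomial numbers of prior walkers in each arm. A stratum in which everyone fails adds nothing to this test.

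| Effect in prior walkers | f | Diluted difference (points) | Unadjusted | Stratified | Gain (points) |
|---|---|---|---|---|---|
| 50% v 80% | 10% | 27 | 70.9% | 77.5% | 7 |
| | 20% | 24 | 60.3% | 72.5% | 12 |
| | 30% | 21 | 49.4% | 66.4% | 17 |
| | 40% | 18 | 38.6% | 59.5% | 21 |
| 50% v 66.6% | 10% | 14.9 | 28.6% | 29.7% | 1 |
| | 20% | 13.3 | 23.7% | 26.9% | 3 |
| | 30% | 11.6 | 19.1% | 24.0% | 5 |
| | 40% | 10.0 | 15.1% | 21.2% | 6 |

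Without the N − 1 factor the smallest gain is 1.7 rather than 1.1 points, so its low end is 1 to 2 points depending on convention. With no non-walkers at all, power is 81.7% and 33.7% respectively.

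**Bonferroni.** At alpha 0.01 (five tests, assumed), 50% versus 66.6% gives 4.9-10.5% unadjusted and 7.4-12.1% stratified, a gain of about 2 to 3 points.

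**Type I error.** With 50% walking in both arms, the stratified test rejects in 5.0% of trials at every f; the unadjusted Z-test rejects in 4.8-5.6%.

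**What stratifying does to the estimate.** Mantel-Haenszel weights are n₁n₀/N. At f = 30%, 28 prior walkers per arm have weight 28 × 28/56 = 14, and 12 non-walkers per arm have weight 12 × 12/24 = 6. With 50% versus 80%, the risk difference is (14 × 30 + 6 × 0)/20 = 21 points, the same as unadjusted. The test gains; the estimate stays diluted.

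**The case against.** The strongest reply is that much of the mechanism is inferred. A reader might take the plan to score every non-walker as a failure in an all-patient denominator. The documents do not say so: the all-randomized sentence is about the primary hypotheses, secondary outcomes get only a statement of similarity, and no scoring rule exists. Nor do the documents show that prior non-walkers must fail. Some may be immobile only because of the limb being removed, and Subject Recruitment says that most of these patients come through the emergency department. This stands. The power figures are therefore an upper case for a given f, and a crude yes/no field would mix two different groups.

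A reader might also infer bias, or that a positive result would merely reflect who walked beforehand. That is not supported. Dilution leaves the test valid under the null, and its type I error already allows for chance imbalance between arms. The all-patient difference is a legitimate quantity to estimate.

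Third, large gains need large effects. At 50% versus 66.6% the comparison is underpowered with or without stratification, and Bonferroni lowers power further. This also stands.

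Finally, restricting to prior walkers might look interchangeable with stratifying. It is not, for a risk difference: restriction gives the undiluted prior-walker effect, while the stratified estimate remains an all-patient one.

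What survives is that a likely strong predictor goes unused, and that using it keeps every randomized patient and holds type I error near 5%.

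**Conclusion.** The point holds as a cheap improvement to one secondary outcome, not as an error in the analysis. Eligibility does not restrict on walking, and the plan indicates an unadjusted comparison that ignores it. The likely consequence is a smaller absolute difference and lower power, without bias under the null.

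The size depends on assumptions that the documents cannot settle. With 10-40% non-walkers who all fail, stratification gains about 7-21 points of power at 50% versus 80%, but only about 1-6 at 50% versus 66.6%. The second range is closer to what the plan's own complication figures could support, given the bridging assumption stated above. Any prior non-walkers who later walk reduce the dilution. The primary conclusion is not touched.

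**What to change.** Record from the chart, at consent or otherwise before assignment is known, whether the patient walked before amputation. Separate immobility due only to the diseased limb from longstanding non-ambulation, and state in advance which stratum each category enters. Consent precedes surgery and patients learn their group only on reaching the floor afterwards, so the timing is feasible.

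State that six-month ambulation is analysed in all randomized patients, with a Cochran-Mantel-Haenszel test and a risk difference stratified on that status. Report the result among prior walkers as a supporting analysis. Because the subgroup is defined by a pre-randomization characteristic, the comparison within it is still randomized.

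Cost: one chart field and one extra analysis. The stratified risk difference remains a diluted all-patient estimate. The prior-walker result applies only to that subgroup, in a smaller denominator.

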This study is being conducted to assess the utility of hyperbaric oxygen as an adjunctive treatment to reduce postoperative complications. It is hypothesized that ${\rm HBO}_2$ given in the immediate postoperative period will reduce postoperative complications in patients undegoing below-the-knee amputations. The objective of this study will be to compare treatment and standard care groups, randomly created of eligible patients, to compare their postoperative complications and to assess their postoperative hospital length of stay, 90-day mortality, failure to heal at 4 and 8 week follow-up visits and ability to ambulate with a prosthesis at 6 months post amputation.

Background & Significance

• Should support the scientific aims of the research

Lower limb amputations (LLA) are commonly performed at Duke University Hospital and are associated with major morbidity, mortality, hospital length of stay and costs. We are proposing a clinical study to test whether hyperbaric oxygen therapy (${\rm HBO}_2$) administered immediately after surgery for ten 2 hour treatments following below knee amputation (BKA) in diabetic patients will reduce surgical site infections (SSIs), reoperations and hospital length of stay (LOS).

LLAs have major morbidity and mortality. Overall, more than 60% of patients who require LLA are diabetic¹. Wound complications occur in 12%, and reoperations in 10-16%, often for infection^{1,2}. Nearly 5% of BKAs require revision to a higher amputation level². Duke University Vascular Quality Initiative (VQI) data indicates that of the 98 LLAs performed at Duke last year 27 resulted in complications, of which 25 needed reoperation. Surgical complications after amputations result in roughly doubling of the cost incurred by hospitals³, thus less than one third of amputations incur almost half of the total cost of amputations.

Both wound healing⁴ and infection risk⁵ are related to the partial pressure of oxygen (PO_2), in affected tissues. Higher peri-wound PO_2 stimulates wound angiogenesis^{6,7} and decreases infection rate⁸. In patients requiring LLA, decreased blood flow due to diabetic microvascular disease and large vessel disease contributes to tissue hypoxia. In this population the combination of hyperglycemia and low tissue PO_2 is the major reason for both poor wound healing and surgical site infection (SSI).

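### Holm's step-down procedure would be a cheap improvement on the planned single-step Bonferroni correction: it never rejects less at the same family-wise limit, though the gain is small unless several outcomes are truly affected

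*Combined protocol and SAP*

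**What the plan says.** The Research Abstract, Design & Procedures and Data Analysis & Statistical Considerations each carry the same sentence: "Bonferroni correction will be used to adjust for multiple tests". No step-down or other sequential version is mentioned, so the ordinary single-step method is the natural reading.

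Design & Procedures names one primary outcome, postoperative complications by the VQI definition. Its secondary outcomes are length of stay, 90-day mortality, failure to heal at 4 weeks and at 8 weeks, and ambulation with a prosthesis at 6 months. For their analysis the plan adds only that "The analysis is similar for secondary outcomes". It then calls 90-day mortality exploratory, although it has just listed it as secondary. The plan does not say which tests form the family, how many there are, or whether the primary is among them.

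Tests are two-sided and no alpha is stated. Differences in proportions "will be estimated along with 95% confidence interval"; no adjusted or simultaneous intervals are promised.

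**The concern.** Single-step Bonferroni compares every p-value in a family of k tests with 0.05/k, however many hypotheses have already been rejected. Holm compares the smallest with 0.05/k, the next with 0.05/(k−1), and so on, stopping at the first failure. Every Holm threshold is at least 0.05/k, so Holm rejects whatever Bonferroni rejects and can reject more. Its family-wise error is bounded by 0.05 whatever the dependence between tests. This holds for any family of two or more.

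The Background argues for a single mechanism, raised wound oxygen acting on both healing and infection. If that is right, more than one outcome may be affected, and Holm could declare some effects that Bonferroni would miss. What is at stake is power for the second and later findings, mostly among the secondary outcomes.

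**Working it through.** **Inputs from the documents.** 40 per arm; effect size 0.62, described as a 60% reduction of complications; local experience ("of the 98 LLAs performed at Duke last year 27 resulted in complications, of which 25 needed reoperation"); at most six outcomes (one primary and five secondary, counting the two healing visits separately), or five if mortality is left out.

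**Assumptions.** Two-sided family-wise alpha 0.05; normally distributed test statistics; all six outcomes in the family; the same effect on every affected outcome. The plan ties 0.62 to complications only ("it is hoped that an effect size of 0.62, or reduction of complications by 60% can be seen").

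**Step 1: the plan's own figure.** The non-centrality is 0.62 × √(40/2) = 2.77. Power at unadjusted two-sided 0.05 is Φ(2.77 − 1.96) = 79%, which matches the stated 80%.

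**Step 2: one test under Bonferroni with k = 6.** Alpha per test is 0.05/6 = 0.0083, with critical value 2.64. Power is Φ(2.773 − 2.638) = 55%.

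**Step 3: Holm thresholds for k = 6.** 0.05/6, 0.05/5, …, 0.05/1 give 0.0083, 0.0100, 0.0125, 0.0167, 0.0250 and 0.0500. The first equals Bonferroni's, so Holm rejects something exactly when Bonferroni does.

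**Step 4: simulation at 0.62.** 200,000 trials per scenario, six tests, independent statistics and correlations of 0.5 to 0.6. Power per affected outcome:

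| Outcomes truly affected | Bonferroni | Holm |
|---|---|---|
| 1 of 6 | 55% | 55% |
| 2 of 6 | 55% | 57% |
| 3 of 6 | 55% | 58% |
| 6 of 6 | 55% | 67% independent; 65–66% correlated |

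With all six affected and independent, the expected number of rejections is 3.3 with Bonferroni and 4.0 with Holm.

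**Step 5: the same at the local rate.** 27/98 = 27.6%; a 60% reduction gives 11.0%. The mean rate is 19.3%, so the non-centrality is 0.1653 / √(2 × 0.1929 × 0.8071 / 40) = 1.87. Bonferroni power is Φ(1.87 − 2.64) = 22%. By simulation Holm gives 22–24% with one to three real effects. With all six it gives 25% if independent and 27–28% at correlations of 0.5 to 0.6.

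**Step 6: error.** With no real effects the family-wise error is the same for both methods: about 4.9% if independent and 4.1% at correlation 0.5. With three of six real and independent at 0.62, the chance of at least one false rejection is 2.5% with Bonferroni and 3.7% with Holm. Both stay below 5%.

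**Step 7: at least one rejection.** The chance is identical under both methods in every scenario, for example 91% with three of six real and independent at 0.62.

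**The case against.** The strongest reply is that nothing is broken. Bonferroni is prespecified, valid and conservative, and replacing it with another valid method is an efficiency suggestion. That stands.

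The second reply is that the attractive figure, 55% v 67%, needs all six null hypotheses to be false at 0.62. That would include 90-day mortality, which the plan itself calls exploratory. No effect size is given for any secondary outcome. This also stands: with one to three real effects the gain is 0 to 3 points.

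The third is that Bonferroni has simple matching simultaneous intervals and Holm's are less simple. True, but the plan specifies only 95% intervals, so nothing it promises is lost.

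The fourth is that the undefined family is the larger gap. Holm does not close it, nor does it repair a sample size that reproduces only at unadjusted 0.05. That stands as well, and is why the fix includes listing the family.

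A reader might also infer that correlated outcomes are where Holm gains most. At 0.62 the simulation shows the reverse: with all six affected, Holm's power falls from 67% when independent to about 65% at correlation 0.6. At the smaller local-rate effect, correlation raises it slightly. What matters is how many effects are real.

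**Conclusion.** The point holds as a low-cost improvement. For any family of two or more tests, Holm does at least as well as the planned method within the same 0.05 limit. Under the stated assumptions the gain in power per affected outcome runs from nothing with one real effect to 10–12 points with all six real at 0.62. At the local complication rate it is smaller throughout.

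A reader might go further and infer that the plan is in error, or that it gives up real findings at no benefit. The documents do not support that. Bonferroni controls the error rate as intended. Holm uses more of the allowed error when some effects are real (2.5% to 3.7% in the three-of-six case). It also cannot help a trial in which no p-value reaches 0.05/k.

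**What to change.** In the Research Abstract, Design & Procedures and Data Analysis & Statistical Considerations, replace the Bonferroni sentence with: *Multiplicity will be handled by Holm's step-down procedure at a two-sided family-wise level of 0.05, and Holm-adjusted p-values will be reported.* Apply it to the same family that the Bonferroni correction was meant to cover.

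List that family by name. Say whether the primary outcome is in it, and settle whether 90-day mortality is secondary or exploratory, since this decides between five and six tests and so fixes the thresholds. Make the change before any between-group comparison of outcomes, including the midpoint analysis mentioned in Design & Procedures.

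The cost is one sentence in three places and a short list. Holm needs only the ordered p-values, which SAS 9.4 can adjust. No extra patients, visits or data are needed. If simultaneous intervals are wanted later, they will take more work than with Bonferroni.
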